## 2. Listing of Demographic and Baseline Characteristics

Output ID: I\_dm\_IT

Center/ Patient ID	Age/Sex/Race	Height [cm]	Weight [kg]	BMI [kg/m  ]	Temperature [C]	Years from First BCC Diagnosis to Dose	Baseline ECOG Performance Status	Gorlin Syndrome	Child Bearing Potential (Females)	Number of Target Lesions at Baseline
xxxxxx/xxx	xx Not Applicable	xxx	xx.x	xx.x	xx.x	x.xx	Grade x	No		x
xxxxxx/xxx	xx Not Applicable	xxx	xxx.x	xx.x	xx.x	xx.x	Grade x	Yes		x
xxxxxx/xxx	xx Not Applicable	xxx	xx.x	xx.x	xx.x	x.xx	Grade x	No	No	x
xxxxxx/xxx	xx Not Applicable	xxx	xx.x	xx.x	xx.x	x.xx	Grade x	No	No	x
xxxxxx/xxx	xx Not Applicable	xxx	xx.x	xx.x	xx.x	x.xx	Grade x	No	Yes	x
xxxxxx/xxx	xx Not Applicable	xxx	xx.x	xx.x	xx.x	xx.xx	Grade x	No	No	x
xxxxxx/xxx	xx Not Applicable	xxx	xx.x	xx.x	xx.x	x.xx	Grade x	No	No	x
xxxxxx/xxx	xx Not Applicable	xxx	xx.x	xx.x	xx.x	x.xx	Grade x	No	No	x
xxxxxx/xxx	xx Not Applicable	xxx	xx.x	xx.x	xx.x	x.xx	Grade x	No	No	x
xxxxxx/xxx	xx Not Applicable	xxx	xx.x	xx.x	xx.x	x.xx	Grade x	No	No	x
xxxxxx/xxx	xx Not Applicable	xxx	xx.x	xx.x	xx.x	x.xx	Grade x	No	No	x
xxxxxx/xxx	xx Not Applicable	xxx	xx.x	xx.x	xx.x	x.xx	Grade x	No	No	x
xxxxxx/xxx	xx Not Applicable	xxx	xx.x	xx.x	xx.x	x.xx	Grade x	No	No	x
xxxxxx/xxx	xx Not Applicable	xxx	xx.x	xx.x	xx.x	x.xx	Grade x	No	No	x
xxxxxx/xxx	xx Not Applicable	xxx	xx.x	xx.x	xx.x	x.xx	Grade x	No	No	x
xxxxxx/xxx	xx Not Applicable	xxx	xx.x	xx.x	xx.x	x.xx	Grade x	No	No	x
xxxxxx/xxx	xx Not Applicable	xxx	xx.x	xx.x	xx.x	x.xx	Grade x	No	No	x
xxxxxx/xxx	xx Not Applicable	xxx	xx.x	xx.x	xx.x	x.xx	Grade x	No	No	x
xxxxxx/xxx	xx Not Applicable	xxx	xx.x	xx.x	xx.x	x.xx	Grade x	No	No	x
xxxxxx/xxx	xx Not Applicable	xxx	xx.x	xx.x	xx.x	x.xx	Grade x	No	No	x
xxxxxx/xxx	xx Not Applicable	xxx	xx.x	xx.x	xx.x	x.xx	Grade x	No	No	x
xxxxxx/xxx	xx Not Applicable	xxx	xx.x	xx.x	xx.x	x.xx	Grade x	No	No	x

Note: Race was recorded as Not applicable in France.

### Programming Note:

- The listing should include patients in the Intent-to-Treat population.
- Please refer to the programming notes for table t\_dm\_\* for definitions of the variables to be displayed in this listing.
- One row per subject.

## 3. Listing of Centers and Countries

Output ID: I\_dm\_inv\_SE

Center	Country
xxxxxxx	UNITED KINGDOM
xxxxxxx	GREECE
xxxxxxx	SLOVAKIA
xxxxxxx	CZECH REPUBLIC

### Programming Note:

- Centers for Safety-Evaluable Patients are included in the Listing.
- Center and Country information comes from Demographic data.
- One row per centre and country.

# Medical History:

## 1. Medical History at Baseline

MHT01	Output ID: t_mh_* 

● Analysis Population: Safety-Evaluatable Patients

● Column Variables: Disease status (Locally Advanced, Metastatic)

● Column Totals: Total of non-missing Disease status

● Analysis Variables: MedDRA System Organ Class, MedDRA Preferred Term.

● Numeric Precision and Formatting of Statistics: Use standard display in the mockup

--------------	---

### Programming Note:

Only display General Medical History (other than BCC) collected on MEDHX CRF page .

## 2. Medical History at Baseline for Patients with an Abnormal ECG Result

MHT01	Output ID: t_mh_ecgabn_* 

● Analysis Population: Safety-Evaluatable Patients

● Column Variables: Disease status (Locally Advanced, Metastatic)

● Column Totals: Total of non-missing Disease status

● Analysis Variables: MedDRA System Organ Class, MedDRA Preferred Term.

● Numeric Precision and Formatting of Statistics: Use standard display in the mockup

● Optional Subsetting: Patients with abnormal ECG results at baseline

--------------	---

### Programming Note:

Only include patients who had an abnormal ECG result at baseline, according to the ECG CRF page.

Only display General Medical History (other than BCC) collected on MEDHX CRF page.

### 3. Medical History Glossary

AEL01_NOLLT	Output ID: I_mh_gloss_SE 

● Analysis Population: Safety-Evaluable Patients

● Column Variables: MedDRA System Organ Class, MedDRA Preferred Term, Lowest Level Term and Reported Term for the Medical History.

● Column Totals: NA

● Analysis Variables: None

● Numeric Precision and Formatting of Statistics: Use standard display in the mockup

--------------------	--

#### Programming Note:

- A glossary of all previous and current medical conditions other than BCC history will be provided.
- Data will be ordered alphabetically by MedDRA System Organ Class, MedDRA Preferred Term, Lowest Level Term and Reported Term for the Medical History.

#### 4. Disease History of Advanced or Metastatic Basal Cell Carcinoma

DMT01
	
Output ID: t_dm_dishis*
 
 
● Analysis Population: Safety-Evaluable Patients
 
● Column Variables: Disease status (Locally Advanced, Metastatic)
 
● Column Totals: Total of non-missing Disease status
 
● Analysis Variables: 
 
1. Diagnosis histologically confirmed               
 
- Yes
 
- No
 
 
 
2. Current disease status               
 
- Metastatic
 
- Locally Advanced                   
 
a) Inoperable
 
b) Surgery Medically Contraindicated                       
 
i) Substantial morbidity and / or deformity
 
ii) Unlikely to be curatively resected
 
iii) Other
 
 
 
 
 
 
 
3. Previously administered radiotherapy               
 
- Yes
 
- No                   
 
a) Contraindicated
 
b) Inappropriate
 
 
 
 
 
4. Measurable Disease Status               
 
- Yes
 
- No
 
 
 
5. Current sites of locally advanced or metastatic disease               
 
- Any Site
 
- Different Disease sites collected on CRF page.
 
 
 
 
 
● Numeric Precision and Formatting of Statistics: Use standard display in the mockup
 

Programming Note:

Refer to CRF Page “Disease History of advanced or metastatic BCC”.

Study MO25616

Page 20 of 104

Output Specifications, Version 1.0

14 September 2015

## 5. Disease History Glossary

AEL01_NOLLT	
Output ID: I_ds_gloss_SE
 

● Analysis Population: Safety-Evaluable Patients

● Column Variables: Current Disease Status, Current Site and Other Specify.

● Column Totals: NA

● Analysis Variables: None

● Numeric Precision and Formatting of Statistics: Use standard display in the mockup

--------------------	---

### Programming Note:

- Investigator text will be used from 'Disease History of advanced or metastatic BCC' CRF page.
- Data will be ordered alphabetically by Current Disease Status, Current Site and Other Specify.

## Concomitant Medication:

### 1. Surgery and Procedures History

#### 1a. Surgery and Procedures History: Non-Cancer Related

CMT01	
Output ID: t_cm_NCANRELSUR_*
 

● Analysis Population: Safety-Evaluable Patients

● Column Variables: Disease status (Locally Advanced, Metastatic)

● Column Totals: Total of non-missing Disease status

● Analysis Variables: Coded INN Class Name Standardized Medication Name

● Numeric Precision and Formatting of Statistics: Use standard display in the mockup

● Optional Subsetting: Select General (Non-Cancer Related) Surgical Procedure History

--------------	--

#### Programming Note:

- Only include records where patient had General (Non-Cancer Related) Surgical Procedure History collected on CRF page "Surgery and Procedures History".

#### 1b. Surgery and Procedures History: Cancer Related

Output ID: t\_cm\_CANRELSURG\_\*

Repeat Output t\_cm\_NCANRELSUR\_\* for Cancer Related Surgery and Procedures History.

#### Programming Note:

- Only include records where patient had Cancer Related Surgical Procedure History collected on CRF page "Surgery and Procedures History".

#### 1c. Prior Medication and Therapies

Output ID: t\_cm\_PRIOR\_\*

Repeat Output t\_cm\_NCANRELSUR\_\* for prior Prior Medication and therapies.

#### Programming Note:

- Only include records where patient had Prior Medication and therapies (concomitant medication started and ended before actual study treatment start) collected on CRF page “Concomitant Medications and Therapies”.

#### 1d. Concomitant Medication and Therapies

Output ID: t\_cm\_CONMED\_\*

Repeat Output t\_cm\_NCANRELSUR\_\* for Concomitant Medication and Therapies.

Programming Note:

- Only select records where patient had Concomitant Medication and therapies (ongoing medication during study treatment) collected on CRF page “Concomitant Medications and Therapies”.

## 2. Prior Therapies

### 2a. Prior Systemic Cancer Therapy Other Than Basal Cell Carcinoma

CMT01	
Output ID: t_cm_SYSNBCC_*
 

● Analysis Population: Safety-Evaluable Patients

● Column Variables: Disease status (Locally Advanced, Metastatic)

● Column Totals: Total of non-missing Disease status

● Analysis Variables: Cancer Therapy, Reason for Discontinuation

● Numeric Precision and Formatting of Statistics: Use standard display in the mockup

● Optional Subsetting: Select Prior Cancer Therapy

--------------	---

#### Programming Note:

- Only include records where patients had Prior Cancer Therapy collected on CRF page "Previous Systemic cancer therapy other than BCC cancer therapy".
- Cancer Therapy and Reason for Discontinuation comes from the Previous Cancer Therapy CRF Page.

### 2b. Prior Cancer Therapy for Metastatic Basal Cell Carcinoma

CMT01	
Output ID: t_cm_prior_mbcc_*
 

● Analysis Population: Safety-Evaluable Patients, Protocol 4 Subset

● Column Variables: Disease status (Locally Advanced, Metastatic)

● Column Totals: Total of non-missing Disease status

● Analysis Variables: Treatment Agent, Reason for Discontinuation

● Numeric Precision and Formatting of Statistics: Use standard display in the mockup

● Optional Subsetting: Select Prior cancer therapy for

--------------	--

	Metastatic BCC
--	----------------

Programming Note:

- Only include records where Patients had Prior cancer therapy for Metastatic BCC collected on CRF page “Previous Systemic cancer therapy for Metastatic BCC”.
- Treatment Agent and Reason for Discontinuation information comes from Prior Cancer Therapy CRF page.

### 2c. Prior Radiotherapy for Metastatic Basal Cell Carcinoma

CMT01	
Output ID: t_cm_rad_mbcc*
 
 
● Analysis Population: Safety-Evaluable Patients, Protocol 4 Subset
 
● Column Variables: Disease status (Locally Advanced, Metastatic)
 
● Column Totals: Total of non-missing Disease status
 
● Analysis Variables: Site, Reason for Administration
 
● Numeric Precision and Formatting of Statistics: Use standard display in the mockup
 
● Optional Subsetting: Select Prior radiotherapy for Metastatic BCC
 

--------------	---

Programming Note:

- Only include records where patients had Prior radiotherapy for Metastatic BCC collected on CRF page “Previous Radiotherapy for advanced or Metastatic BCC”.
- Site and Reason for Administration information comes from CRF.

### 3. Listing of Concomitant Medication Glossary

AEL01_NOLLT	
Output ID: l_cm_gloss_SE
 
 
● Analysis Population: Safety-Evaluable Patients
 
● Column Variables: Class Term, Standardized Medication and Reported Name of Drug, Med or Therapy.
 
● Column Totals: NA
 

--------------------	--

	
 
● Analysis Variables: None
 
● Numeric Precision and Formatting of Statistics: Use standard display in the mockup
 

--	--

**Programming Note:**

- Output includes anti-cancer therapy for subjects with any of the following AE preferred terms ongoing at treatment discontinuation and still ongoing 12 months after treatment discontinuation: Muscle Spasm; Ageusia; Dysgeusia; Alopecia; Weight Decrease.

**5. Listing of Anti-Cancer Treatment for Subjects with AEs Ongoing at Treatment Discontinuation, and Still Ongoing at 12 Months after**

Study MO25616

Page 26 of 104

### Programming Note:

- Output includes anti-cancer therapy for subjects with any of the following AE preferred terms ongoing at treatment discontinuation and still ongoing at last assessment: Muscle Spasm; Ageusia; Dysgeusia; Alopecia; Weight Decrease.

# Histology:

Output ID: t\_histol\_SE

	Locally Advanced (N=xxxx)	Metastatic (N=xxxx)	Total (N=xxxx)
Histologically confirmed Disease			
Yes	xxxx (xx.x%)	xx (xx.x%)	xxxx (xx.x%)
No	x (x.x%)	x (x.x%)	xx (x.x%)

## Programming Note:

- N = Number of patients present in each disease status category i.e. Locally Advanced or Metastatic.
- Histology confirmation comes from PDMS system - i.e. Subjects included in the PDMS system for a deviation of 'Non-histologically confirmed disease' will be included in the 'No' category.
- Include Safety Evaluable Patients.

## Disease Progression prior to Study:

Output ID: t\_di\_prog\_IT\_PV4ANY

	Locally Advanced (N=xxx)	Metastatic (N=xx)	Total (N=xxx)
Documentation of Disease Progression			
Radiographic	xx (xx.x%)	xx (xx.x%)	xx (x.x%)
Clinical	x ( x.x%)	x ( x.x%)	x (x.x%)
Histological	x ( x.x%)	x ( x.x%)	x (x.x%)
Newly Diagnosed mBCC			
Yes	xx (xx.x%)	xx (xx.x%)	xx (x.x%)

### Programming Note:

- N is Number of Patients in the Intent-to-Treat population with Protocol 4 Subset (consented to Protocol version 4 or higher at any time).
- Percentages should be based upon N.
- Documentation of Disease Progression and Newly Diagnosed mBCC information comes from 'Documentation of Progression prior to Enrolment' CRF page.

## Symptom Status of Metastatic Patients:

### Summary of Symptom Status of Metastatic Patients:

STREAM Template	Description
N/A	Output ID: t_mbcc_symp_* 
 
● Analysis Populations: Safety, Excluding Patients with Baseline MDASI Score
 
● Column Variables: Disease Status (Metastatic)
 
● Column Totals: None
 
● Analysis Variables: n, Symptomatic, Non-Symptomatic
 
● Statistics and Calculation Methods: Use proq freq for events or proc sql for patient counts.
 
● Numeric Precision and Formatting of Statistics: N/A
 
● Optional Subsetting: None.
 

Summary of Symptom Status of Metastatic Patients, Population : Safety-Evaluable Patients  
 Protocol: MO25616  
 Snapshot Date: 03 August 2015. Clinical Cut-Off Date: 16 March 2015.  
 File: t\_mbcc\_symp\_SE.

	Metastatic (N=96)
n	96
Symptomatic	31 (32.3%)
Non-Symptomatic	65 (67.7%)

Note: Symptom Status was adjudicated by the Sponsor following medical review of baseline symptom data.

#### Programming Note:

- Symptom status was defined via Sponsor (Clinical Science) manual review of the data as to whether the subject was symptomatic or not. Details of this are in the DAP M3.

## Protocol Violations:

Protocol Violations (PVs) will be taken from the PDMS (Protocol Deviation Management System) and reviewed by Clinical Science. All major Protocol Violations will be summarised and Listed. At the request of the Science team, the Cut-off date should not be used with Violations as the date of the Violations according to the system are the dates that the violation was input, not the date that the violation occurred. Clinical Science reviewed the file to ensure that all correct violations are included and reported.

STREAM Template	Description
MHT01	Output ID: t_pv* 
 
● Analysis Population: Safety
 
● Column Variables: Disease Status (Locally Advanced, Metastatic)
 
● Column Totals: Totals of non-missing Disease Status
 
● Analysis Variables: Total Patients with at least one Deviation, Total number of Inclusion Criteria Violations, Total number of Procedural Violations, Total number of Medication Violations, Total number of Exclusion Criteria Violations
 
● Statistics and Calculation Methods: Use proc freq for individual violations or proc sql for patient counts.
 
● Numeric Precision and Formatting of Statistics: Use standard display in the mockup
 
● Optional Subsetting: For each Category of Violations, include the counts for each individual Violation.
 

PDL01	Output ID: l_pv* 
 
● Analysis Population: Safety
 
● Column Variables: Use Standard STREAM columns
 
● Numeric Precision and Formatting of Statistics: Use standard display in the mockup
 

## Output Specifications: Safety Outputs

### Exposure:

Capsules are dispensed to each subject at the time of each visit and are recorded on the CRF. Subjects take a dose of 150 mg daily and fill in any missed dose dates on the Patient Diary, in case of dose missed for any reason. The investigator completes the number of capsules taken between visits on the basis of number of capsules returned by the subject at the next visit.

It is possible for a subject to have taken all the dispensed capsules between two visits and still have a missed dose if there is a delay in scheduling or attending the next visit. Consider the total number of capsules dispensed, taken, and the missed dosing date for daily dose calculation (ie, consider the sum of all dispensed/taken doses).

#### 1. Overall Summary of Exposure to Study Medication (Vismodegib)

EXT01	Output ID: t_ex_SE 

● Analysis Population: Safety-Evaluable Patients

● Column Variables: Disease Status (Locally Advanced, Metastatic)

● Column Totals: Totals of non-missing Disease Status

● Analysis Variables: Summary Statistics

○ Number of days missed dose

○ Cumulative dose of Vismodegib

○ Duration on treatment (in days)

○ Dose intensity

○ Total doses

● Numeric Precision and Formatting of Statistics: Use standard display in the mockup

--------------	---

#### Programming Note:

- The number of days of missed dose (and so the number of missed doses) will be calculated as follows: The number of days between the first and last dose, minus the sum of the number of capsules taken according to the Dose Accountability CRF page. i.e. If first dose was the 1st Jan, and the last dose

as the 28th Feb, and the subject had taken 55 capsules (according to their 'taken' records, then there would be 4 (59-55) missed doses.

- Cumulative dose of Vismodegib will be calculated as the sum of the total number of capsules taken (recorded on the Dose Accountability CRF page) at each visit multiplied by 150 mg.
- Duration on treatment will be calculated as time from first dose date to last dose date (last dose date minus first dose date + 1), measured in days.
- Dose intensity will be calculated as the sum of the total number of capsules taken (recorded on the Dose Accountability CRF page) at each visit / sum of the total number of capsules dispensed (recorded on the Dose Accountability CRF page) at each visit x 100.

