The M.D. Anderson Symptom Inventory (MDASI) will be used to assess the impact of treatment on symptoms in metastatic BCC patients enrolled after approval of the Study Protocol, version 4.0. For these metastatic patients, incidence and type of disease symptoms will be summarized at baseline. In addition, the number of metastatic BCC patients with 30% reduction in disease-related symptoms with baseline score of 4 or more at any time during treatment will be summarized for each symptom.

Exploratory Pharmacokinetic Assessments

Individual and mean plasma vismodegib concentration versus time data will be tabulated and plotted. Plasma AAG concentration and unbound plasma concentration at selected time points will be estimated, tabulated and summarized (geometric mean, mean, standard deviation, coefficient of variation, median, minimum, and maximum). Additional PK analyses may be conducted as appropriate.

Determination of Sample Size

Approximately 1200 patients will be enrolled in this study.

Synopsis Table 1. Clopper-Pearson 95% Confidence Intervals for the observed AE incidence¹

Number of AE events/ observed AE incidence	95% Clopper Pearson Confidence Interval
12 (1%)	0.5% – 2%
24 (2%)	1.3% – 3.0%
60 (5%)	3.8% – 6.4%
120 (10%)	8.4% – 11.8%
240 (20%)	17.8% – 22.4%
360 (30%)	27.4% – 32.7%

¹ Total number of patients is 1200

Therefore, for a sample size of 1200 patients, the true AE incidence rate can be estimated to within 1.6%–1.8% assuming an observed incidence of 10%, i.e., within 95% Clopper-Pearson confidence interval of 8.4%–11.8%.

Treatment scheme:

[figure not shown]

Table 1 Schedule of Assessments

Cycle	Screening / Baseline	Treatment Phase ¹ (Allowed Visit Window +/- 3 days from Cycle 2 onwards)								End of Treatment Visit ²	Safety Follow-Up Visits ³ (1 month, 3 months, 6 months, 9 months, 12 months after the last dose of vismodegib (GDC-0499))
		1	2	3	4	5	6	7	8 onwards		
Day	-28 to -1	1	29	57	85	113	141	169	Every 28 Days		
Informed Consent ⁴	X										
Archival Tumor Tissue ⁵	X										
Medical History and Demographics ⁶	X										
Complete Physical Examination	X										
Limited Physical Examination ⁷		X	X	X	X	X	X	X	X	X	
Height ⁸ and Weight	X	X	X	X	X	X	X	X	X	X	
Vital Signs ⁹	X	X	X	X	X	X	X	X	X	X	
ECG	X	As clinically indicated								X	
ECOG Performance Status	X	X	X	X	X	X	X	X	X	X	
Hematology	X	X ¹⁰	X	X	X	X	X	X	X	X	X (if clinically indicated)
Biochemistry	X	X ¹⁰	X	X	X	X	X	X	X	X	X (if clinically indicated)

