Record Date of Last Menses ¹¹	X	X	X	X	X	X	X	X	X	X	X
Pregnancy Test ¹²	X	X	X	X	X	X	X	X	X	X	
Serum Hormone Evaluation ¹³	X	As clinically indicated								As clinically indicated	As clinically indicated
Steady-state and post-treatment pharmacokinetic collection of blood (AT SELECTED SITES ONLY) ²⁴		One collection while taking vismodegib for at least 2 weeks continuously									At 3, 6, 9, and 12 Months ONLY
QoL Assessments using Skindex-16 (in selected sites)	X		X					X		X	

Table 1 Schedule of Assessments (cont.)

Cycle	Screening / Baseline	Treatment Phase ¹ (Allowed Visit Window +/- 3 days from Cycle 2 onwards)								End of Treatment Visit ²	Safety Follow-Up Visits ³ (1 month, 3 months, 6 months, 9 months, 12 months after the last dose of vismodegib (GDC-0499))
		1	2	3	4	5	6	7	8 onwards		
Day	-28 to -1	1	29	57	85	113	141	169	Every 28 Days		
Symptom Assessment using MDASI ¹⁴	X	X	X	X	X	X	X	X	X	X	X
Tumor Assessments (physical examination) ^{15, 17}	X	Every 4 to 8 weeks from the time of the first dose (±5 days) regardless of dosing delays.								X	
Tumor Assessments (by imaging techniques, if required) ^{16, 17}	X	Every 8 to 16 weeks from the time of the first dose (±5 days) regardless of dosing delays or as per institutional standards In metastatic BCC patients (newly enrolled after approval of the Study Protocol, version 4.0), every 8 weeks from time of first dose (±5 days) regardless of dosing delay								X	
AEs / SAEs ¹⁸	X	X								X	X
AE-related pharmacokinetic collection of blood (AT SELECTED SITES ONLY) ²⁵											At 6, 9, and 12 Months ONLY
Ultrasound ¹⁹	X	As clinically indicated								As clinically indicated	As clinically indicated
Follow-up for disease progression		X								X	X
Tumor biopsy and collection of whole blood ²⁰										X	
Concomitant medication	X ²¹	X								X	X
New anti-cancer therapy										X	X
Drug Dispensing		X (first day of each Cycle)									
Drug Accountability ²² Drug Dosing Exception Diary ²³			X	X	X	X	X	X	X	X	X

Table 1 Schedule of Assessments (cont.)

Notes Results of screening tests or examination performed as standard of care before obtaining informed consent and within the specified interval may be used rather than repeating required evaluation. Day 1 = first dose of study drug vismodegib.

1. Visits during the treatment period are to be completed on Day 1 of every 28-Day Cycle.
2. End of Treatment Visit will be performed when the patient discontinues vismodegib regardless of when it occurs.

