6. INVESTIGATIONAL MEDICINAL PRODUCT (IMP)

6.1 DOSE AND SCHEDULE

Enrolled patients will receive continuous once-daily oral dosing of vismodegib at a dosage of 150 mg per administration. One cycle of therapy is defined as 28 days of treatment. Dose reduction of vismodegib is not permitted, as there is only a 150-mg capsule strength available.

Dosing of vismodegib will continue until one of the following occurs:

- Investigator-assessed disease progression
- Unacceptable toxicities most likely attributable to vismodegib
- Patient consent withdrawal
- Death
- Reasons deemed by the treating physician
- Study termination by the Sponsor

If there is objective evidence of progressive disease, but the Investigator believes the patient is still deriving benefit from treatment, treatment with vismodegib may be continued after consultation with the medical monitor. However, if there is evidence of further disease progression at the next tumor assessment, vismodegib should be discontinued.

At each study visit, patients will be given enough capsules for dosing until the next study visit. The Investigator is required to confirm that any female patient of childbearing potential has a negative pregnancy test, understands the teratogenic potential of vismodegib, and is using an effective method of contraception prior to dispensing vismodegib. Patients will be instructed to take one 150 mg capsule per day.

Vismodegib should be taken at approximately the same time each day, with or without food. Capsules must be swallowed whole and must not be opened under any circumstances. If a patient misses a dose (e.g., due to emesis), he or she should be instructed not to take or make up that dose and to resume dosing with the next

scheduled dose. Missed doses will not be made up. Patients will be instructed to bring all unused capsules to each study visit for assessment of compliance.

If a patient is suspected to be pregnant, vismodegib must be immediately discontinued. If it is subsequently confirmed that the patient is not pregnant, dosing may be resumed.

The terminal half-life of vismodegib has been determined to be 10–14 days in humans, based on preliminary findings in healthy patients. If plasma concentrations of vismodegib need to be lowered emergently, animal studies suggest that oral administration of activated charcoal may lower plasma drug levels more quickly than dose cessation alone.

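### SAP dose intensity divides capsules taken by capsules dispensed, so it measures use of supplied stock and not the share of the planned daily dose received

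*SAP*

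**What the plan says.** The SAP's overall summary of exposure lists "Dose intensity" beside missed-dose days, cumulative dose, duration on treatment and total doses. The Programming Note takes the numerator as total capsules taken and the denominator as the "sum of the total number of capsules dispensed (recorded on the Dose Accountability CRF page) at each visit x 100".

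The same note counts missed doses against the calendar: "The number of days between the first and last dose, minus the sum of the number of capsules taken". Its worked example runs from 1 January to 28 February with 55 capsules taken and gives 4 missed doses. Duration is last dose date minus first dose date plus 1.

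The introduction to the SAP Exposure section says: "It is possible for a subject to have taken all the dispensed capsules between two visits and still have a missed dose". This can happen when the next visit is delayed.

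The protocol plans one 150 mg capsule daily without dose reduction (6.1, 6.1.1). On supply, 6.1 says only that "patients will be given enough capsules for dosing until the next study visit". Table 1 puts dispensing on the first day of each 28-day cycle, with the header "Allowed Visit Window +/- 3 days from Cycle 2 onwards". Section 6.3 gives 32 capsules per bottle and allows for different local packaging. Unused capsules are brought back "to each study visit for assessment of compliance" (6.1).

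**The concern.** A reader who sees dose intensity in an exposure table will probably read it as the percentage of the planned dose received while on treatment. The formula gives the percentage of supplied capsules that were used. The two can differ in either direction:

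- **Too low.** Spare capsules in a bottle, or a supply left unfinished when treatment stops, count as dose not received.
- **Too high.** Days on which the patient had no capsules add nothing to the denominator. In the situation the SAP itself describes, the formula returns 100% over an interval with missed doses.

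Dose reduction is barred and missed doses are not made up, so missed days and interruptions are the way received dose falls below plan during treatment. Those are the days the formula can overlook. Protocol 8.1.1 lists exposure among the primary variables, and the adverse event tables will be read against it.

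**Working it through.** **Inputs.** Planned dose: 1 capsule per day (protocol 6.1). Cycle: 28 days (6.1). Bottle: 32 capsules (6.3). Visit window: ±3 days (Table 1). Interruption: up to 8 weeks, or 56 days (6.1.1). Worked example: 1 January to 28 February, 55 taken (SAP Programming Note). The number dispensed per visit is not stated, so every dispensed figure below is an assumption.

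**The SAP's own figure.** Inclusive days from 1 January to 28 February are 58 + 1 = 59, and 59 − 55 = 4 missed doses, as stated. The plain difference of 58 would give 3, so the example counts days inclusively.

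**Identity.** SAP ratio = taken / dispensed = (taken / days) × (days / dispensed). The first factor is the share of planned dose. The ratio equals it only if dispensed = days.

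**The example patient.** Share of planned dose = 55/59 = 93.2%. The SAP ratio for the same patient is:

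| Assumed dispensed | SAP ratio | Difference from 93.2% |
|---|---|---|
| 55 | 100.0% | +6.8 points |
| 56 (2 × 28) | 98.2% | +5.0 |
| 59 | 93.2% | 0.0 |
| 64 (2 × 32) | 85.9% | −7.3 |
| 84 (3 × 28) | 65.5% | −27.7 |
| 96 (3 × 32) | 57.3% | −35.9 |

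The last two rows apply if a third supply was given at the scheduled Day 57 visit. The window would allow that visit as late as Day 60, so two dispensings are also possible.

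**Too low, full adherence.**
- One 32-capsule bottle per cycle, leftovers still counted as dispensed: 28/32 = 87.5% at any treatment length.
- 28 per cycle plus one unused final supply of 28: 56/84 = 66.7% after 2 cycles, 168/196 = 85.7% after 6, 364/392 = 92.9% after 13.

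**Too high.**
- 28 given and the next visit 3 days late: SAP 28/28 = 100%, planned share 28/31 = 90.3%.
- 168 days on treatment including a 56-day break, 28 capsules per cycle and nothing dispensed in the break: SAP 112/112 = 100%, planned share 112/168 = 66.7%.

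**Where the result depends on dispensing.**
- Same break, but capsules dispensed and returned while still counted as dispensed: SAP 112/168 = 66.7%, which agrees with the planned share.
- Visit 3 days late, but 32 given and 31 taken: SAP 31/32 = 96.9%, planned share 31/31 = 100%. The error changes sign.

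**The case against.** The strongest reply is that nothing here contradicts the protocol. Section 8.2.2 asks for cumulative dose and frequency tables by cycle or week, and dose intensity is an extra row with an explicit formula. Taken over dispensed is a recognisable accountability measure, in keeping with how protocol 6.1 and 6.6.2 assess compliance. Missed days, duration and cumulative dose sit in the same table and do not use the dispensed count. Treatment breaks and adverse events leading to interruption are reported elsewhere. The larger discrepancies need particular dispensing patterns. No section names 28 as a quantity, and a 32-capsule bottle would cover a visit three days late. The table mock-up is not available, so a clarifying footnote may exist.

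Much of this stands: the effect is confined to one descriptive row, its size is unknown, and the examples are illustrations and not bounds.

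The neighbouring rows do not remove the defect. They are separate summaries, and the distribution of each patient's share of planned dose cannot be recovered from them, because a ratio of means is not a mean of ratios. That the formula is explicit does not make the label right.

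The reply also says the replacement is imperfect, and that is true. The last dose date is taken from the date drug is returned (SAP, Definition of Last Dose). A bottle returned 14 days late with no missed dates recorded would turn 168/168 = 100% into 168/182 = 92.3%, whereas taken over 168 dispensed would still give 100%. The duration and missed-dose rows already carry that same error.

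**Conclusion.** The concern holds. As written, the row labelled dose intensity does not measure dose received against dose planned, and it need not agree with the missed-dose row in the same table. The upward error follows from the SAP's own statement about using up all dispensed capsules. The downward error follows whenever more capsules are dispensed than there are treatment days.

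The size cannot be determined. It depends on three things the documents leave open: capsules given per visit, dispensing during breaks, and whether returns are subtracted from the dispensed count. No test, sample size or efficacy estimate is affected. It should still be corrected, because exposure is a primary variable in this safety trial and the correction needs no new data.

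**What to change.** Define dose intensity (%) = total capsules taken / (last dose date − first dose date + 1) × 100. Both quantities are already derived in the same Programming Note. With missed days counted inclusively, as in the SAP's example, the result equals 100 × (1 − missed days / duration), so the rows reconcile by construction: 55/59 = 93.2% = 100 × (1 − 4/59).

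If taken over dispensed is wanted, keep it under the name drug accountability and state how returned capsules enter the dispensed count.

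Either change costs one line of SAP text and code. The new denominator inherits any error in the return-based last dose date, so a footnote should say so.
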